14.2.4.5 Lymphocyte proliferative response

Principle

In addition to antigen specific responses, possible changes in vaccination induced systemic lymphocyte responses will be measured by analysing lymphocyte proliferation in response to co- culture with the vaccine in vitro. This assay serves as a marker for general immune-competence of the patient. Such in vitro proliferative responses of both CD4 and CD8 T cells were monitored in the Phase I study that has been completed with DCP-001, and showed an increase after vaccination in a number of patients.

Description

To assess the immune competence of patients pre and post vaccination, the lymphocyte proliferative response will be evaluated by incubating patient derived fluorescent dye labelled PBMC with graded doses of irradiated stimulator cells (DCOne derived mDC and progenitor cells) in round-bottom, 96- well plates in triplicates for 3-6 days. A positive vaccination-induced response is defined as an increase in Post-Vaccination proliferation of $\geq 10\%$. Supernatants of all samples will be collected for exploratory cytokine analysis using a luminex bead-based multiplex assay.

14.2.4.6 Immunohistochemistry (IHC) on biopsies

Principle

To obtain more insight in the immune cells infiltrating the injection site, punch biopsies will be taken from the injection site 2 days after the first vaccination, 4th vaccination, and the second booster vaccination. The cellular infiltrate will be analysed by hematoxylin-eosin (HE)staining IHC in order to characterise the inflammatory cell populations by digital quantification that allows quantitative, standardised and calibrated image acquisition.

Description

A hematoxylin-eosin (HE) staining will be performed on two tissue slides located just before and after the last IHC slide. A pathologist will provide a morphological evaluation of the two HE tissue slides. IHC will be performed for each biopsy on serial slide sections. Based on a review of IHC slides by a pathologist either a semi-quantitative analysis (scoring), or a computer-assisted approach (digital image analysis) will be performed.

14.3 PHARMACOKINETICS

Not applicable.

14.4 ADHERENCE TO PROTOCOL

14.4.1 Treatment Compliance

As this study involves intradermal administration of the study medication administered by trained study personnel, patient compliance measures are not necessary. The quantity of study medication administered to the patient will be recorded in the eCRF at each visit.

14.5 TERMINATION OF THE STUDY BY THE SPONSOR

The study may be terminated prematurely in case of the occurrence of serious, unexpected adverse events, necessitating a review of the product's safety profile. Also, unforeseen events or new information relating to the product, making it unlikely that the objectives of the study or clinical programme will be met, may warrant the sponsor to discontinue the study prematurely.

The Sponsor reserves the right to discontinue the study at any time for failure to meet expected enrolment goals and therefore it will not be possible to reach study objectives, in the interests of safety, or any other administrative reasons e.g. in those cases that compliance to the clinical protocol can no longer be guaranteed. The Sponsor shall take advice from the data and safety monitoring committee as appropriate in making this decision.

In case the study is ended prematurely, the sponsor will notify the Relevant Competent Authorities and ECs and will including the reasons for the premature termination.

15 ADVERSE EVENTS AND OTHER SAFETY ASPECTS

15.1 DEFINITION OF AN ADVERSE EVENT

An adverse event (AE) is any undesirable physical, psychological or behavioural effect experienced by a patient during participation in an investigational study, in conjunction with the drug or biologic, whether or not product-related. This includes any untoward signs or symptoms experienced by the patient from the time of signing of the informed consent until completion of the study.

AEs may include, but are not limited to:

- subjective or objective symptoms spontaneously offered by the patient,
- and/ or observed by the investigator or medical staff,
- findings at physical examinations,
- laboratory abnormalities of clinical significance.

Disease signs, symptoms, and/or laboratory abnormalities already existing prior to the use of DCP-001 are not considered AEs after treatment unless they reoccur after the patient has recovered from the pre-existing condition or in the opinion of the investigator they represent a clinically significant exacerbation in intensity or frequency.

Clinical significance is defined as any variation in signs, symptoms, or testing that has medical relevance and may result in an alteration in medical care. The investigator will continue to monitor the patient until the assessment returns to baseline or until the investigator determines that follow-up is no longer medically necessary.

Worsening of the patient's condition for which the study treatment is being used is not considered an AE.

15.2 DEFINITION OF A SERIOUS ADVERSE EVENT

A serious AE (SAE) is any AE that results in the following outcomes:

- results in death,
- life threatening experience,
- required or prolonged inpatient hospitalization,
- persistent or significant disability/incapacity,
- congenital anomaly,
- important medical events, that based upon appropriate medical judgement, may jeopardize the patient and may require medical or surgical intervention to prevent one of the outcomes listed above.

15.3 ADVERSE EVENT REPORTING

The investigator is responsible for monitoring the safety of patients who have enrolled in the study and for accurately documenting and reporting information as described in this section.

Patients will be instructed to report to the investigator any AE they experience. Investigators will ask about the occurrence of AEs at each visit. Investigators are required to document all AEs occurring during the clinical study, commencing with signing of the informed consent through the protocol defined end of study.

Adverse events will be scored according to the NCI Common Terminology Criteria for Adverse Events, version 4.0.

The causal relationship of AEs to study treatment will be determined by the Investigator and adjudicated by the MM. Drug-related causality will be defined as events that are definitely related, probably related, or possibly related to study drug. Events will be categorized as unrelated to study drug if they are reported as not related. The following list will be used to assist with the assessment of causality:

Definitely Related: The AE is clearly related to the investigational agent/procedure, i.e., an event that follows a reasonable temporal sequence from administration of DCP-001, follows a known or expected response pattern to the suspected drug, that is confirmed by improvement on stopping and reappearance of the event on repeated exposure and that could not be reasonably explained by the known characteristics of the subject's clinical state.

Probably related: When there is a temporal relationship to the study drug administration, significant symptoms abate upon discontinuation of DCP-001 and there is a reasonable explanation based on known characteristics of the study drug and there is no clear association with pre-existing disease or therapy, intercurrent illness, concurrent therapy, or other factor(s).

Possibly related: An event that follows a reasonable temporal sequence from the administration of DCP-001, follows a known or expected response pattern to the suspected drug, but that could readily have been produced by a number of other factors.

Not related: The AE is clearly not related to the investigational agent/procedure. Another cause of the event is most plausible; and/or a clinically plausible temporal sequence is inconsistent with the onset of the event and the study medication administration; and/or a causal relationship is considered biologically implausible. Concurrent illness, concurrent medication or other known cause is clearly responsible for the AE.

The action taken with study treatment will be reported according to the following options: Dose not changed, Dose reduced, Drug interrupted, Drug withdrawn, Not applicable, and Unknown.

In accordance with international regulatory requirements, there is a separate reporting system for SAEs.

15.4 DOCUMENTATION OF NON-SERIOUS ADVERSE EVENTS

All AEs occurring following the signature of the informed consent will be recorded. All AEs will be recorded in designated eCRF pages and source medical recorded.

15.5 REPORTING OF SERIOUS ADVERSE EVENTS

In case of a SAE, the investigator should contact Linical Accelovance, by telephone, email or fax within 24 hours of the first knowledge of the event even if the experience does not appear to be related to the study drug (contact details to be used: Linical Accelovance Drug Safety (using the SAE Cover Sheet Report Forms – in the SAERP) to Linical Accelovance's SAE dedicated [contact] or [contact]). See also page 8.

Full details of the SAE should be recorded on the observation notes and on the eCRF.

The investigator must also complete an SAE Report, containing all information that is required by Regulatory Authorities. The completion of this SAE Report is therefore mandatory for SAEs.

All correspondence on SAEs has to be marked URGENT. The following minimum information is required:

- Study number
- Patient identification number, sex, and year of birth
- The name and address of the reporting person (in confidence)
- A description of the SAE

The sponsor will report expedited the serious unexpected serious adverse reactions (SUSARs) to the IEC:

- SUSARs that have arisen the clinical study that was assessed by the IEC;
- SUSARs that have arisen in another clinical study of the same sponsor and with the same medicinal product, and that could have consequences for the safety of the patients involved in the clinical study that was assessed by the IEC.

The remaining SAEs will be reported to the IEC on half yearly basis in form of line listings, accompanied by a brief report highlighting the main points of concern.

The sponsor will report all SUSARs on expedited basis to the competent authorities.

The expedited reporting will occur not later than 15 calendar days after the sponsor has first knowledge of the adverse reactions. For fatal or life threatening cases the term will be a maximum of 7 calendar days for a preliminary report with another 8 days for completion of the report.

15.6 EXPECTED SIDE EFFECTS OF STUDY MEDICATION

Results from numerous clinical trials with DCs indicate that DC-based immunotherapy is safe and well-tolerated. There may be a slight discomfort due to the local skin reaction following injection.

15.7 FOLLOW-UP OF CLINICALLY SIGNIFICANT ADVERSE EVENTS

All AEs will be followed until they have abated, or until the investigator determines that follow-up is no longer medically necessary. Depending on the event, the follow up may require additional tests or medical procedures as indicated, and/or referral to the general physician or medical specialist.

15.8 DATA SAFETY MONITORING BOARD

The DSMB will meet per the DSMB Charter.

The primary responsibility of the Data Safety Monitoring Board (DSMB) is to ensure safety of patients prior to administration of the next vaccination of DCP-001. The DSMB consist of qualified experts in the disease area but are otherwise independent of the study. In case of doubt regarding the interpretation of any AEs, responsible investigators will on the shortest notice report the issue to the medical monitor who will consult with the DSMB, at least in case of any SAE determined to be related to DCP-001 administration. The DSMB will review each SAE and all severe laboratory abnormalities as rapidly as possible and provide advice whether the study can reasonably continue. Other AEs, including laboratory data which may indicate toxicity, will be reviewed periodically. The DSMB will discuss, analyse on the issue, and report to the investigator and the sponsor. Ultimately the sponsor will decide whether the study should be discontinued (section 14.6).

16 STATISTICAL METHODS

16.1 DETERMINATION OF SAMPLE SIZE

Recruitment will target 20 patients greater than 18 years of age with a confirmed diagnosis of AML that are in CR1 or CRi with MRD. The planned sample size of 20 evaluable subjects will be distributed 1:1 with 10 subjects each in Group 1- 25E6 DCP-001 cells per vaccination, and Group 2- 50E6 DCP-001 cells per vaccination. Additional subjects may be enrolled to ensure that 20 evaluable subjects complete the study. As the impact of vaccination on MRD levels is the primary endpoint, strict sample size statistical considerations with a desired power for a pre-specified difference is not yet possible. However, assuming that 90% of patients in the overall (untreated) population will experience MRD, a sample size of 20 subjects is sufficient to detect a 22% difference between the treated group and the overall population, using a one sample, two-tailed z-test of proportion with 80% power and a 5% level of significance. No formal sample size calculations were completed for this study.

16.2 STATISTICAL AND ANALYTICAL PLANS

No inferential analysis is planned for the study; only descriptive analyses will be used. In general, descriptive statistics, unless otherwise noted, will include the number of subjects, mean, standard deviation, median, minimum value, and maximum value, and where applicable, 95% confidence intervals. Percentages will be calculated using the number of evaluable subjects within each treatment group. If appropriate, immune monitoring data will be summarized using the geometric mean, standard error of the geometric mean, and 95% confidence intervals of the geometric mean. Unless otherwise stated, all summary tables will present descriptive statistics and/or frequency by visit for each treatment group. The analysis will be performed on the data collected up to the last MRD assessment (Day 224).

All statistical analyses and data summaries will be completed using SAS Software (version 9.2 or greater).

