6 SYNOPSIS

| | |
|--|---|
| Name of Sponsor/Company: DCprime bv | |
| Name of Investigational Product: DCP-001 | |
| Name of Active Ingredient: The active ingredient consists of allogeneic human dendritic cells (DCs) derived from the CD34+ progenitor AML cell line, DCOne. These DCs endogenously express several AML specific leukemia associated antigens (LAA) that include WT1, MUC1, PRAME and RHAMM. | |
| Title of Study: Allogeneic Dendritic cell Vaccination in AML oNgoing Clinical Evaluation II | |
| Short Study Title (acronym): ADVANCE II | |
| Study center(s): Approximately 3-5 sites Countries: Netherlands, Germany | |
| Coordinating Investigators: [name]. [name] | |
| Studied period (years): Recruitment time: 12 - 18 months. Treatment time: 4.5 months Follow up time: 12 months after the last patient receives the last biweekly (4 th) vaccination. Total Study duration: approximately 34 months | Phase of development: IIa, Proof of Concept |
| Rationale: Immunotherapy offers promise in AML and has created opportunities for improved outcomes. Dendritic cell (DC)-based immunotherapy has shown to be a promising strategy for the elimination of minimal residual disease (MRD) in patients with acute myeloid leukemia (AML). DCP-001 is an allogeneic dendritic cell based immunotherapeutic vaccine that expresses a number of tumour antigens that are expressed in AML and have shown clinical results when applied as peptide vaccines or loaded onto patient derived DC. Evidence for DCP-001 mediated safety, feasibility and immunological responses have been demonstrated in a Phase I study; the current study aims to generate evidence for clinical efficacy. | |
| Objectives: Primary: 
 • To assess the effect of DCP-001 on MRD. MRD will be measured by flow cytometry pre and post vaccination as a surrogate marker for established clinical endpoints in AML. • To assess the effect of DCP-001 on immune responses in AML patients in first complete remission (CR1) and persistent MRD. • To document safety and tolerability. | |

| |
|---|

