| 
Secondary:
 
• To identify surrogate (immunological) markers that might correlate with clinical outcome.• To quantify any lag time between initiation of treatment & onset of effect.• To determine the effect of DCP-001 on Time to Relapse (TTR).• To determine the effect of DCP-001 on Overall Survival (OS) during the study.• To document the difference between the two vaccination regimens based on MRD outcome and immunological parameters. |
| 
Methodology:
 
International, multicentre, open-label proof of concept study without randomization and stratification. Two different dose groups are included. Group 1 consists of 10 patients that will receive 25E6 DCP-001 cells per vaccination with two additional booster vaccinations of 10E6 cells. Group 2 consists of 10 patients who will receive 50E6 DCP-001 cells per vaccination with two additional booster vaccinations of 10E6 cells.
 
Patients will be screened for eligibility for the study and evaluated at baseline, at each vaccination visit and every 8 weeks during follow up. Each patient will be followed up for 12 months after the 4th vaccination. Sera and cell samples (blood and bone marrow) will be collected when indicated for efficacy (MRD evaluation) and immune response monitoring.
 |
| 
Number of patients (planned):
 
No less than 20 patients are planned for participation
 |
| 
MRD assessment:
 
MRD will be determined at start of the vaccination, prior to the first boosting vaccination, after the last boosting and a final MRD assessment will be performed 100 days after receiving the last boost (day 224). MRD will be determined with multi-parametric flow cytometry. Flow cytometric MRD is based on leukaemia associated phenotype (LAP) that will be established at diagnosis and at specified time points post-vaccination. MRD will be reported as a percentage of the whole white blood cell compartment in complete remission, according to standardized protocols. Assessment of MRD will be performed by a central lab (VUmc).
 |

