7 FLOW CHART AND SCHEDULE OF ASSESSMENTS

Table 1: Flowchart and assessment schedule

| | Screening | Baseline wk 0 | wk 0 | wk 2 | wk 4 | wk 6 | wk 6 | wk 11 | wk 14 | wk 18 | wk 18 | wk 20 | wk 32 | FU ¹ +8 weeks | End of Study ² (Final FU Visit) |
|--|-----------|--------------------|----------------|-----------------|-----------------|-----------------|-----------------|-----------------|-----------------|------------------|------------------|------------------|------------------|--------------------------------|---|
| days | -28 | 0 | 2 ⁷ | 14 ⁸ | 28 ⁸ | 42 ⁸ | 44 ⁷ | 77 ⁸ | 98 ⁸ | 126 ⁸ | 128 ⁷ | 140 ⁸ | 224 ⁸ | | |
| Visit No. | 1 | 2 | 3 | 4 | 5 | 6 | 7 | 8 | 9 | 10 | 11 | 12 | 13 | 14-17 | 18 |
| Informed consent | √ | | | | | | | | | | | | | | |
| Inclusion/exclusion criteria | √ | | | | | | | | | | | | | | |
| Demographics | √ | | | | | | | | | | | | | | |
| Medical History | √ | | | | | | | | | | | | | | |
| Physical examination | √ | √ | | √ | √ | √ | | √ | √ | √ | | √ | √ | √ | √ |
| ECOG | √ | √ | | √ | √ | √ | | √ | √ | √ | | √ | √ | √ | √ |
| HLA Typing ¹¹ | √ | | | | | | | | | | | | | | |
| Vital signs | √ | √ ³ | | √ | √ | √ | | √ | √ | √ | | √ | √ | √ | √ |
| ECG, X-thorax | √ | | | | | | | | | | | | | | |
| Haematology ⁴ | √ | √ ³ | | √ | √ | √ | | | √ | √ | | √ | √ | √ | √ |
| Biochemistry ^{5, 13} | √ | √ ^{3, 13} | | √ | √ | √ | | | √ | √ | | √ | √ | √ | √ |
| Urine analysis ¹⁰ | √ | | | | | | | | | | | | | | √ |
| Viral tests (HIV, Hepatitis B and C) ¹² | √ | | | | | | | | | | | | | | |
| MRD assessment (BM aspirate) | | √ | | | | | | | √ | | | √ | √ | | |
| DCP-001 Vaccination | | √ | | √ | √ | √ | | | √ | √ | | | | | |
| Immunomonitoring | | √ | √ | | | | √ | √ | | | √ | √ | √ | | |
| Skin biopsy ⁹ | | | √ | | | | √ | | | | √ | | | | |
| End of treatment | | | | | | | | | | | | | √ | | |
| End of study | | | | | | | | | | | | | | | √ |
| Prior and Concomitant medication | √ | √ | √ | √ | √ | √ | √ | √ | √ | √ | √ | √ | √ | √ | √ |
| Adverse event reporting ⁶ | | √ | √ | √ | √ | √ | √ | √ | √ | √ | √ | √ | √ | √ | √ |

- 1) Follow up visits on wk 40, 48 and 56
- 2) End of study visit (last FU visit) will be performed 12 months after 4th vaccination, or, no more than 2 weeks after last treatment received if a patient goes off study before week 32
- 3) If baseline assessment is within 7 days of first vaccination and if results meet the stated eligibility criteria, these assessments need not to be repeated on day 0

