9.1.2 Secondary Objective(s)

1. To identify surrogate (immunological) markers that might correlate with clinical outcome.
2. To quantify any lag time between initiation of treatment & onset of effect.
3. To determine the effect of DCP-001 on Time to Relapse (TTR).
4. To determine the effect of DCP-001 on Overall Survival (OS).
5. To document the difference between the two vaccination regimens based on MRD outcome and immunological parameters.

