Upon completion of the treatment phase each patient will enter the follow up phase. The patient will return every 8 weeks (\pm 2 weeks) up to 12 months after 4th vaccination. The following assessments will be performed at each follow up visit;

- Physical examination, ECOG and Vital signs
- Hematology and biochemistry
- Record any new AEs, SAEs and concomitant medications and/or changes in ongoing AEs, SAEs and ongoing concomitant medications

Subsequent follow up visits will occur at least every 8 ± 2 weeks until end of study (i.e. 12 months after 4th vaccination) or disease progression.

End of study visit (18) / 12 months after last vaccination

- Physical examination, ECOG and Vital signs
- Perform study specific hematology and biochemistry
- Urine analysis
- Record any new AEs, SAEs and concomitant medications and/or changes in ongoing AEs, SAEs and ongoing concomitant medications

See schedule of assessment (Table 1) for study specific procedures.

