16.2.3 Analysis of Efficacy Variables

MRD levels and immune responses will be summarized descriptively by treatment group and visit as described above. Time to event variables (e.g. time to relapse) will be analysed using survival analysis techniques (e.g, Kaplan-Meier estimates).

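### The Day 224 data cut is stated for the whole analysis; read as a study day, it leaves out 45% of each patient's planned follow-up for time to relapse and overall survival, and the end-of-study date also needs reconciling

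*Protocol*

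**What the plan says.** Section 16.2 sets one data cut: "The analysis will be performed on the data collected up to the last MRD assessment (Day 224". The statistical paragraph of the synopsis repeats it and goes on to the Kaplan-Meier analysis of time-to-event variables. Section 16.2.3 names the method, "Time to event variables (e.g. time to relapse) will be analysed using survival analysis techniques", and gives no other cut-off.

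The secondary objectives in 9.1.2 include "To determine the effect of DCP-001 on Time to Relapse (TTR"), and OS is listed next to it. The synopsis words the second as "To determine the effect of DCP-001 on Overall Survival (OS) during the study".

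On length of follow-up, the synopsis has "Follow up time: 12 months after the last patient receives the last biweekly (4 th) vaccination", and footnote 2 of Table 1 has "End of study visit (last FU visit) will be performed 12 months after 4th vaccination". The follow-up text of section 14.1 uses the same 4th-vaccination anchor twice. The heading for visit 18 in that section reads "End of study visit (18) / 12 months after last vaccination". Table 1 numbers the follow-up visits 14 to 17, while its footnote 1 says "Follow up visits on wk 40, 48 and 56".

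**The concern.** The cut falls on the last MRD visit, which suits MRD and the immune assays, because no marrow or immunomonitoring sample is scheduled later. It does not suit TTR and OS, whose events continue to accrue in the follow-up phase. The sentence speaks of the analysis as a whole and names no exception, so a literal reading keeps every relapse and death after Day 224 out of the two secondary endpoints that the follow-up visits exist to serve.

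What is at stake is whether the trial can describe relapse and survival at 12 months. The sentence also does not say whether Day 224 is each patient's study day or the calendar date on which the last patient reaches it, and the size of the loss depends on that.

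**Working it through.** **Schedule days.** Week 32 in Table 1 gives 32 × 7 = Day 224, which reproduces the protocol's cut-off. The 4th vaccination is at week 6 (Table 1 and section 12.3): 6 × 7 = Day 42. Taking 12 months as 365 days, follow-up ends at 42 + 365 = Day 407 (week 58).

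**Reading A: Day 224 is each patient's study day.** This is how Table 1 uses the term.
- Days lost: 407 − 224 = 183.
- Share lost: 183/407 = 45.0% (182/406 = 44.8% if 12 months is 364 days).
- Day 365 lies beyond the cut, so no 12-month estimate exists for TTR or OS.

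**Can a median TTR still be reached under reading A?** Assume exponential relapse from Day 0, with a proportion p relapsed by Day 365. The median is 365 × ln 2 / (−ln(1 − p)).
- The median equals Day 224 when 1 − p = 0.5^(365/224) = 0.32, so p is about 68%.
- At p = 80%: 365 × 0.693/1.609 = about Day 157, before the cut.
- At p = 60%: 365 × 0.693/0.916 = about Day 276, after the cut.

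Section 8.2 gives relapse rates of 60-80% but no time horizon, so the protocol does not settle which case applies.

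**Reading B: the calendar date of the last patient's Day 224.** Assume uniform accrual over R days, with R = 365 or 548 (the synopsis gives 12 to 18 months). Let L be the days between Day 224 and end of study. A patient enrolled t days before the last one loses L − t days if t < L, and otherwise none, so the mean loss is L²/(2R).

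| End of study | L | Mean loss, R = 365 | Mean loss, R = 548 |
|---|---|---|---|
| Day 407 | 183 | 45.9 days (11.3%) | 30.6 days (7.5%) |
| Day 491 | 267 | 97.7 days (19.9%) | 65.0 days (13.2%) |

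**The end-of-study date.** The visit 18 heading counts from the last vaccination.
- Last booster at week 18 (Table 1, sections 12.3 and 14.1): Day 126 + 365 = Day 491, which is 126 − 42 = 84 days after Day 407.
- Section 12.4 puts the boosters on Days 77 and 98: Day 98 + 365 = Day 463, which is 56 days after Day 407.

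Two other items fit the later date better.
- Total duration is given as about 34 months. Counting 18 months of recruitment, the anchor day and 12 months gives 18 + 42/30.4 + 12 = 31.4 months from the 4th vaccination, and 18 + 126/30.4 + 12 = 34.1 months from a Day 126 booster.
- Four 8-weekly visits after week 32 fall at weeks 40, 48, 56 and 64, and week 64 is past week 58. Footnote 1 lists only the first three.

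**The case against.** The strongest reply is that little rides on this. Section 16.2 plans no inference, there are 20 non-randomised patients, and the primary outcomes are untouched: MRD and immune samples end at Day 224, and treatment-emergent events close 30 days after the last vaccination. Full analysis detail is left to the statistical analysis plan, and section 19.6 requires a final report within a year of the last patient's last visit, so a later TTR and OS analysis may well be intended. The part about consequence stands and lowers the severity. The part about intent does not remove the problem: the cut is stated twice without qualification, and an analysis plan that used later data would depart from the protocol's text.

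Some stronger conclusions are tempting, but the documents do not support them.
- A reader might infer that no median TTR can be reported. It can, if early relapse is high enough.
- A reader might put the loss at 54% (267/491) and treat the 84-day gap as settled. Both rest on one heading, which the follow-up text of the same section contradicts twice, and on a booster day that section 12.4 dates differently.
- A reader might infer that the two end dates change patients' censoring times. While the Day 224 cut stands as a study day, both lie beyond it and affect no estimate.
- A reader might attach a share of relapses or deaths to the lost period. The protocol gives no relapse or survival rate over time from which to derive one.

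**Conclusion.** The point holds and should be fixed. Followed as written, with Day 224 as a study day, the plan drops 183 of 407 days (45%) of each patient's follow-up from TTR and OS and rules out 12-month figures for both. That percentage rests on the 4th-vaccination anchor, which most sections use, and on 12 months being 365 days. If a calendar cut is meant, the mean loss is about 8-11% (13-20% with an end at Day 491) under uniform accrual, and 12-month estimates remain possible. The protocol does not say which is meant.

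The end-of-study conflict is real but secondary. It matters for how long sites follow patients, and for TTR and OS once the cut is lifted.

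**What to change.** **Data cut.** In section 16.2 and the synopsis, limit the Day 224 cut to MRD, immune response and treatment-emergent adverse events, and say whether Day 224 is a study day or a calendar cut. State that TTR and OS are analysed on all follow-up to the end of study, with Day 224 figures as an earlier description.

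**Data collection.** Confirm that survival status is recorded after progression. Section 14.1 stops follow-up visits at end of study or at progression, whereas section 12.5 asks patients who leave treatment to enter follow-up. If status is not recorded, a later OS analysis needs more than a wording change.

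**End of study.** Reconcile the anchor across the synopsis, Table 1 and section 14.1. Make visit numbers 14 to 17, the listed weeks 40, 48 and 56, and the 34-month duration agree with it. The booster days in Table 1 and sections 12.3, 12.4 and 14.1 must also be reconciled.

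**Cost.** Protocol wording, one later Kaplan-Meier run, and possibly a survival-status item after progression. The final TTR and OS report would come later than the Day 224 report.
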